Patients will continue on lenalidomide maintenance for 24 months unless they develop progressive disease or unacceptable toxicity. The initial dose of maintenance therapy will be 10 mg of lenalidomide daily. We plan to adjust the dose according to specific dose modification criteria. To monitor response during lenalidomide maintenance, we will obtain post-ASCT imaging scan prior to starting lenalidomide and then every three months during the first year and every 4 months during the second year.

STUDY ENDPOINTSPrimary:

Dose limiting toxicity (DLT) as assessed by NCI CTCAE version 4.0

Secondary:

Progression free survival

Overall survival

STUDY DURATION: 60 months

DOSING REGIMEN: The initial dose of lenalidomide will be 10 mg daily. We will use a 3+3 design to determine tolerability of this dose in these heavily pretreated patients. We will allow decreasing lenalidomide to 5 mg daily according to specific dose modification criteria. We will stop the study if there are 2 subjects with DLTs at the 5 mg dose level.

TOTAL SAMPLE SIZE: We plan to enroll 24 evaluable patients with relapsed/refractory lymphoma who will initiate lenalidomide maintenance after ASCT during the initial 3 years of the study. It is likely that at least 28 patients may be enrolled to provide 24 evaluable patients.

DRUG SUPPLIES: Celgene Corporation will provide lenalidomide at no charge through the Revlimid REMS® program for study participants.

2 Schedule of Study Assessments

Procedure	Screening	Cycle 1			Cycles 2-24*	Discontinuation From Protocol Therapy	Follow-Up Phase
	On day 28-100 after ASCT at hematological recovery (<28 days before starting maintenance)	Day 1 [^]	Day 15	Day 22	Day 1		Every 3 months ⁸
Informed Consent	X						
Record lymphoma diagnosis, current medications	X						
Record prior anti-cancer therapies	X						
Physical examination, vital signs, weight	X	X ⁶	X		X	X	
ECOG performance status	X	X ⁶	X		X	X	
Imaging (PET/CT or CT scan)	X				X ⁴		
ECG	X						
CBC	X	X ⁶	X	X	X	X	
Serum chemistries ¹	X	X ⁶	X		X		
Pregnancy testing ^{2,3}	X	X ⁶			X	X	
Register patient into Revlimid REMS® program	X						
Baseline lesion assessment	X						
Prescribe lenalidomide via Revlimid REMS® ⁷	X				X		
Response assessment ⁴					X ⁴	X ⁴	
Record adverse events			X		X	X ⁵	
Record concomitant therapies/procedures		X			X	X	
Assess drug compliance/patient's study calendar					X	X	
Follow-up anti-cancer treatments							X
Follow-up progression and survival information							X

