5.3.6 Study Discontinuation

The following will be performed at the time of study discontinuation, whether due to study completion or early withdrawal from study participation

- Physical Exam and evaluation of ECOG PS
- Vital signs (Blood pressure, heart rate, temperature, weight)
- CBC with differential and platelets
- Serum chemistry panel including sodium, potassium, chloride, CO₂, calcium, serum creatinine, BUN, total bilirubin, alkaline phosphatase, AST, ALT and TSH
- Assessment of adverse events and concomitant medications

5.3.7 Safety Assessment (to be performed 28 Days (+/- 7 days) after study discontinuation)

- Assessment of adverse events and concomitant medications

5.3.8 Follow-Up (to be performed every 3 months for the first 3 years after study discontinuation, and then yearly thereafter)

- Review of anti-cancer treatments
- Review of progression and survival information

Assessments to be performed at screening and during scheduled study visits are also outlined in Section 2 Table of Study Assessments.

At treatment discontinuation, subjects will undergo off study evaluations per the Schedule of Assessments, Section 2. In addition, a safety assessment will be done approximately 28 days after the last dose of protocol therapy. Follow-up contact with the subjects should occur at a minimum of 3 months during the first 3 years after finishing maintenance phase and annually after that.

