5.7 Discontinuation of Study Treatment

Study treatment will continue until the completion of 24 cycles of lenalidomide maintenance therapy, or the occurrence of any of the following events:

- Disease progression (See Appendix D)
- Adverse event(s) that, in the judgment of the Investigator, may cause severe or permanent harm or which rule out continuation of the treatment regimen.
- Discontinuation or interruption in lenalidomide therapy for ≥ 28 consecutive days.
- Withdrawal of consent
- Lost to follow up
- Death
- Pregnancy or a positive pregnancy test

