10.3 Endpoints

Dose-limiting toxicity (DLT) is defined as any grade 3 toxicity or higher that occurs during the first 28 days of therapy and is possibly, probably or definitely related to lenalidomide maintenance. Because certain levels of toxicity are considered acceptable in lymphoma therapy, the definition of DLT is limited to the following:

-Any grade 3 or higher non-hematologic toxicity possibly, probably or definitely related to lenalidomide.

-Grade 4 hematologic toxicity not attributable to progressive disease and that does not decrease to a grade 3 or less within 7 days of drug cessation.

-Lymphopenia of any grade and anemia of any grade are not considered a DLT.

-Nausea and vomiting are not considered DLTs unless they cannot be controlled with standard antiemetic therapy.

-Diarrhea is not considered a DLT unless it cannot be controlled with standard anti-diarrheal therapy.

-Nausea, vomiting, heartburn, anorexia, diarrhea, or constipation that improved to grade 1 or better within 2 days with the addition of symptom directed treatment will not be considered a DLT.

NCI Common toxicity criteria (CTC Version 4.0) grades will be employed. Toxicity unrelated to lenalidomide (i.e. clearly related to ASCT) will be scored separately.

Progression-free survival (PFS) is defined from date of ASCT (day 0) to first documented progression of disease, death due to any cause or last patient contact. Progression-free survival rate at 12 months (PFS12) is also of interest and is defined as the percentage of patients that are alive and progression-free at 12 months. Overall survival (OS) is defined as days from date of ASCT to death due to any cause or last patient contact.

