Patients are enrolled 28 to 100 days after ASCT (day 0). Patients who complete one full cycle of lenalidomide maintenance or who experience DLT during the first cycle will be considered evaluable for DLT determination. Patients who withdraw from the study prior to initiation of lenalidomide maintenance, or who initiate and discontinue lenalidomide maintenance before completing one full cycle and do not experience DLT, remain in the study population and are followed for PFS and OS but do not contribute to the determination of DLT. These patients will be included in the estimation of PFS and OS, according to an intent-to-treat analysis plan. A secondary analysis of PFS and OS will include only patients who complete at least one full cycle of lenalidomide or who experience DLT at any point during cycle 1 (“evaluable population”). Patients who did not progress will be censored at the time of last contact. Evaluable patients contribute to determination of DLT, PFS and OS. Evaluable patient outcomes will be compared to historical rates for PFS12.

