10.6 Plans for Data Analysis

All observed toxicities will be graded and tabled. The toxicities may be stratified as either related to lenalidomide or other medications (i.e. high dose chemotherapy and ASCT). Progression-free survival and overall survival will be estimated by the method of Kaplan and Meier. A minimum of 12 months of observation time is required on all patients (or less if patient has failed), in order to estimate PFS12. The PFS12 rate and 95% confidence interval will be computed. In addition to the observed rate and 95% CI, evidence for success of lenalidomide will be assumed if >4 of 24 evaluable patients are alive and progression-free at 12 months, based on operating characteristics defined by binomial probabilities. The probability of observing >4 patients alive and progression-free in 24 patients when true rate is 10%, is 0.09 (false positive rate). The probability of observing ≤4 patients alive and progression-free when true rate is 30%, is 0.11 (false negative rate).

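### With PFS censored at last contact, an evaluable patient who stops lenalidomide early can count as a 12-month success although no imaging or examination is clearly scheduled after the stop

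*Combined protocol and SAP*

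**What the plan says.** - **PFS definition (Section 10.3).** PFS runs "from date of ASCT (day 0) to first documented progression of disease, death due to any cause or last patient contact". The same section adds: "Patients who did not progress will be censored at the time of last contact".
- **Follow-up for PFS12 (Section 10.6).** "A minimum of 12 months of observation time is required on all patients", or less after failure. No scan, examination or window around month 12 is named.
- **Decision rule (Section 10.6).** "evidence for success of lenalidomide will be assumed if >4 of 24 evaluable patients are alive and progression-free at 12 months". Section 10.7 sizes the trial on this comparison (10% against 30%).
- **Who is evaluable (Section 10.3).** The evaluable population is "patients who complete at least one full cycle of lenalidomide or who experience DLT at any point during cycle 1".
- **Stopping without progression (Section 5.7).** Reasons include adverse events and "interruption in lenalidomide therapy for ≥ 28 consecutive days".
- **After stopping.** The Section 2 schedule marks a response assessment at discontinuation, and Sections 5.3.8 and 5.8 adopt that schedule. The follow-up column then has "Follow-up progression and survival information" every three months, and Section 5.3.8 words it as "Review of progression and survival information". Neither lists imaging or a physical examination.
- **Imaging.** Section 5.3.5 and footnote 4 of Section 2 tie scans to maintenance. Section 5.1 leaves imaging to discretion only once two years of follow-up have passed, and Section 7 refers to study participation while counting in cycles.

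**The concern.** Contact shows that a patient is alive. It does not show that the lymphoma has not progressed. While a patient is on drug, scans every three cycles and a visit each cycle make the two nearly the same, and nothing is claimed about those patients. They come apart for a patient who completes a cycle, stops for toxicity or a long interruption, and is then known only through a review of information.

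Two results are exposed. The >4 of 24 count can include such a patient as a success on contact alone, and the Kaplan-Meier curve credits the unassessed months as progression-free. The count needs only five successes, so single patients matter. It is also the only stated efficacy criterion. Because the plan does not say how an early stopper without a later assessment is counted, that choice could be made after the data are seen.

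**Working it through.** **1. The plan's own figures.** Success means at least 5 of 24.
- P(Bin(24, 0.10) ≥ 5) = 0.0851 (stated 0.09).
- P(Bin(24, 0.30) ≥ 5) = 0.8889 (stated 89% power; false-negative rate 0.111, stated 0.11).

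The stated figures reproduce.

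**2. Length of the gap.** Lenalidomide starts on day s = 28 to 100 after ASCT (Section 10.1). A patient who stops at the end of cycle 1 stops on day s + 28, that is day 56 to 128. The time left to day 365 is 365 − (s + 28), which is 309 days for s = 28 and 237 days for s = 100.

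**3. Effect on the rule.** The documents give neither the number of early stoppers nor the chance m that a progression after stopping goes undocumented by month 12, so both are assumed. Take a true PFS12 of 10%. An early stopper then counts as a success with probability q = 0.10 + 0.90m, and everyone else with probability 0.10.
- One early stopper: q × P(Bin(23, 0.10) ≥ 4) + (1 − q) × P(Bin(23, 0.10) ≥ 5) = 0.1927q + 0.0731(1 − q).
- Two: q² × P(Bin(22, 0.10) ≥ 3) + 2q(1 − q) × P(Bin(22, 0.10) ≥ 4) + (1 − q)² × P(Bin(22, 0.10) ≥ 5) = 0.380q² + 2 × 0.172q(1 − q) + 0.0621(1 − q)².

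| m | q | one early stopper | two |
|---|---|---|---|
| 25% | 0.325 | 0.112 | 0.144 |
| 50% | 0.55 | 0.139 | 0.213 |
| 100% | 1 | 0.193 | 0.380 |

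The nominal level in Section 10.7 is 10%. At the 7% rate that Section 3.1 reports for PET-positive patients, the base is 0.023 and two early stoppers give 0.05, 0.09 and 0.20.

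**4. Effect on Kaplan-Meier PFS12.** If nobody is censored before month 12, the estimate is the proportion free. With one progression certain to be missed, its mean is (1 + 23 × 0.10)/24 = 0.1375; with two, (2 + 22 × 0.10)/24 = 0.175. Simulation (20,000 trials) gave 0.137 and 0.173 with last-contact censoring, and 0.100 in both cases with last-assessment censoring.

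**5. Patients lost before month 12.** Section 10.6 does not say how they count, so the direction is open. If 10% have unknown status and are counted as failures, P(Bin(24, 0.27) ≥ 5) = 0.82 and P(Bin(24, 0.09) ≥ 5) = 0.059, which makes the rule conservative.

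**6. Would an assessment requirement penalise patients on drug?** Scans fall at day s + 84j. Without delays, the last scan at or before day 365 is at most 83 days earlier. The worst case is s = 30, with scans on day 282 and day 366. One 12-week interval before month 12, extended for permitted visit windows and dose delays, therefore covers on-schedule patients. A symmetric window of ±6 weeks would not: with the ±7 days of Section 2, the nearest scan can be 49 days away, and 13 of the 73 possible start days can fall outside 42 days.

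**The case against.** A reader might infer that early stoppers have no disease follow-up at all. The documents do not support that. Section 2 marks a response assessment at discontinuation, and Sections 5.3.8 and 5.8 adopt it even though the list in 5.3.6 omits it. Progression information is reviewed every three months. Footnote 4 of Section 2 lets progression rest on the clinical picture as well as imaging. Section 10.3 keeps even patients who stop before finishing a cycle in follow-up for PFS and OS. Section 7 calls for monthly examinations throughout study participation, and Section 5.8 uses that term in a way that can include time off drug. The gap is thus partly a conflict of wording. What stands is that a review of information requires no scan or examination, and no passage settles what applies after an early stop.

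A reader might also treat every cycle 1 DLT as an early stop. Table 2 in Section 5.5.3 mostly holds and restarts lenalidomide. It specifies removal only for grade 4 or desquamating rash and grade 4 neuropathy. The exposed group is therefore smaller than the DLT count.

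The larger figures assume that progression is never documented. Section 5.1 says that the imaging schedule reflects usual practice outside the trial, which makes certain misses less likely. This objection stands, and it is why the sizes are only illustrations.

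Finally, PFS is secondary, and last-contact censoring in a 24-patient single-arm trial can be called convention. That lowers the priority. It does not remove the undefined count in the efficacy rule.

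**Conclusion.** The point holds in a limited form. An evaluable patient who stops early without progression and stays in contact can be credited as progression-free at 12 months without a disease assessment after the discontinuation visit. Among patients still in contact, the error runs one way: more successes and a higher Kaplan-Meier PFS12. One such patient would move the false-positive rate from 0.085 to between 0.11 and 0.19, and two to between 0.14 and 0.38, under assumed miss rates of 25% to 100% and a true rate of 10%.

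These figures do not show that the stated operating characteristics are wrong; those reproduce. Nor do they show a net bias against the historical controls, because the documents do not give the scan schedule or follow-up of that group. The primary endpoint, DLT, is untouched. This is a cheap improvement.

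**What to change.** 1. **Censoring (both statements in Section 10.3).** End PFS for non-progressors at the last disease assessment without progression. Keep death from any cause as an event and leave OS at last contact. Report how many are censored before 12 months. This corrects progression that is never documented, but not progression first found late. In a simulation with early stoppers' progression dated to day 390, mean PFS12 at a true 0.10 stayed at about 0.12–0.13 with one and 0.14–0.16 with two. So also report the number first found after a gap longer than one scheduled imaging interval, with a sensitivity analysis that dates them as failures by 12 months.
2. **Decision rule (Section 10.6).** Count a success only if the patient is alive at 12 months, has no progression documented by then, and has a progression-free assessment either after 12 months or within one scheduled imaging interval before it (12 weeks plus permitted visit windows and dose delays). A first assessment after stopping that shows progression does not qualify. All others, including patients lost before 12 months, stay in the 24 as non-successes and are reported by number. A sensitivity analysis counts them as progression-free.
3. **Data collection.** For patients off lenalidomide without progression, collect reports of routine scans until progression or 12 months after ASCT.
4. **Reconciliation.** Footnote 4 of Section 2 and Sections 5.1, 5.3.5, 5.3.6 to 5.3.8 and 7 must be made consistent on whether the assessment schedule continues after lenalidomide stops. Which reading applies is for the sponsor.

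**Cost.** Items 1 to 3 need only wording and collection of existing reports; item 4 could affect imaging, depending on how it is resolved. Power falls from 0.889 to P(Bin(23, 0.30) ≥ 5) = 0.864 with one unassessed patient, or P(Bin(22, 0.30) ≥ 5) = 0.835 with two. The false-positive rate falls to 0.073 or 0.062. Censoring at last assessment assumes that stopping is unrelated to later progression, which is why the number censored early must be shown.

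### The PFS censoring sentence in Section 10.3 omits the condition that the patient is alive; applied as written, it would censor deaths without progression and bias the Kaplan-Meier PFS curve upward

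*Combined protocol and SAP*

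**What the plan says.** Section 10.3 measures PFS from the date of transplant "to first documented progression of disease, death due to any cause or last patient contact". Three end points stand in one list, and the sentence does not mark which are events and which is the censoring point. PFS12 is "defined as the percentage of patients that are alive and progression-free at 12 months". For OS the section says: "Overall survival (OS) is defined as days from date of ASCT to death due to any cause or last patient contact".

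Later in Section 10.3, after the definition of the evaluable population, comes the only sentence in the documents that uses the word censored: "Patients who did not progress will be censored at the time of last contact".

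Section 10.6 says how these endpoints are used. "Progression-free survival and overall survival will be estimated by the method of Kaplan and Meier". For the 12-month rate: "A minimum of 12 months of observation time is required on all patients (or less if patient has failed), in order to estimate PFS12". Success is assumed "if >4 of 24 evaluable patients are alive and progression-free at 12 months".

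**The concern.** The censoring sentence and the PFS definition can give different event indicators for the same patient. Take a patient who dies of sepsis in month 5 with no documented progression. Under the definition, PFS ends with an event in month 5. Under the censoring sentence the patient did not progress, so the observation is censored.

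Such deaths are foreseeable. Section 3.3 accepts that severe cytopenias are a valid worry when lenalidomide is given early after transplant, and Section 3.2 lists sepsis, pneumonia, myocardial infarction and pulmonary embolism among reported adverse events.

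Censoring these deaths turns the curve into an estimate of time to progression while it is still labelled PFS. It would remove the fatal events that count against a maintenance drug. Two analysts working from the same section could also produce different curves.

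**Working it through.** **1. The plan's own design figures.** Inputs from Sections 10.6 and 10.7: n = 24, success at 5 or more, null rate 10%, alternative 30%. Exact binomial:

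- P(X ≥ 5 | n = 24, p = 0.10) = 0.0851. The plan gives the false positive rate "when true rate is 10%, is 0.09 (false positive rate"), which agrees after rounding.
- P(X ≤ 4 | n = 24, p = 0.30) = 0.1111, against the stated 0.11. Power = 1 − 0.1111 = 0.8889, against the stated 89%.

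The count includes only patients who are alive without progression at month 12. A patient who has died is a failure however the Kaplan-Meier data are coded, so these figures do not depend on the censoring sentence.

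**2. Bias in the Kaplan-Meier curve if the sentence is followed literally.** Let S be the true PFS at 12 months, with deaths counted as events. Let d be the proportion of all patients who die without progression by month 12. The documents do not give d; 5% to 15% is an assumption. Also assume constant cause-specific hazards, with the two causes independent.

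- Total cumulative hazard to month 12: H = −ln(S).
- Share of events that are deaths without progression: f = d / (1 − S).
- Value that Kaplan-Meier estimates with those deaths censored: exp(−H × (1 − f)) = S^(1 − f).

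For S = 0.20 and d = 0.10: H = 1.609, f = 0.10 / 0.80 = 0.125, and exp(−1.609 × 0.875) = 0.245.

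| True PFS at 12 months | d = 5% | d = 10% | d = 15% |
|---|---|---|---|
| 10% | 11.4% | 12.9% | 14.7% |
| 20% | 22.1% | 24.5% | 27.0% |
| 30% | 32.7% | 35.6% | 38.8% |

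A simulation of 4,000 trials with n = 24, S = 0.20 and f = 0.125 gave a mean 12-month Kaplan-Meier estimate of 0.199 with deaths as events and 0.244 with deaths censored.

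**3. The median.** With constant hazards the median is 12 × ln(2) / H months, and censoring the deaths divides it by (1 − f). For S = 0.20 and d = 10%: 12 × 0.693 / 1.609 = 5.2 months, which becomes 5.2 / 0.875 = 5.9 months.

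**4. A small worked case.** Take 24 patients. Twelve progress first; then 2 die without progression while 12 are at risk; of the remaining 10, 5 progress before month 12 and 5 do not.

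- Deaths as events: 5/24 = 20.8%.
- Deaths censored: (12/24) × (5/10) = 25.0%.
- Count for the success rule: 5 under either coding.

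**The case against.** The strongest reply is that the definition earlier in Section 10.3 already settles the matter. It lists death and last contact as separate end points, and the censoring sentence reuses the term for last contact. Read together, a patient who dies reaches the death end point, and last contact applies only to patients with neither progression nor death. This is the more natural reading, and nothing in the documents shows an intent to censor deaths. It does not remove the conflict, because the definition does not say which of its three end points are events and the one sentence that states a censoring rule leaves death out.

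A reader might infer more than the documents support:

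- **That the efficacy decision is inflated.** It is not. The success rule and the PFS12 definition both require patients to be alive. Section 10.6 refers to an observed rate with at least 12 months of observation on every patient who has not failed, which points to a simple proportion. Section 10.3 compares evaluable patients with historical rates for PFS12, so that comparison is also untouched.
- **That OS is affected.** The censoring sentence stands in a paragraph that covers both endpoints, but OS is defined by death and makes no reference to progression. A progression-based rule is naturally about PFS.
- **That the bias is of known size.** It is not. Entry requires hematologic recovery between days 28 and 100 after transplant, so earlier transplant deaths never enter the cohort, and the upper part of the assumed range is harder to presume. The shift in the worked case, 25.0 − 20.8 = 4.2 points, is also small beside the exact 95% interval for 5/24, roughly 7% to 42%.

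All three limits stand. They narrow the point but do not remove it.

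**Conclusion.** The point holds as a wording defect with a limited statistical consequence. Followed literally, the censoring sentence conflicts with the PFS definition in its own section and biases a named secondary endpoint upward. The exposure is the Kaplan-Meier PFS curve, its median and any 12-month value read from it.

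The size depends on an assumed rate of death without progression and on the hazard assumptions stated above. Over 5% to 15% by month 12, the upward shift is about 1 to 5 points at a true 10%, 2 to 7 points at a true 20%, and 3 to 9 points at a true 30%. If no patient dies without progression, the two codings give the same curve.

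This is not evidence that the sponsor plans to censor deaths. It should still be corrected, because the written rule is what an analyst would program.

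**What to change.** Replace the censoring sentence in Section 10.3 with: *For PFS, patients who are alive without documented progression will be censored at last contact; death from any cause without prior progression is a PFS event on the date of death.*

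The cost is one sentence. No design figure changes and no additional data are needed, since survival is already followed under Section 5.8. The Kaplan-Meier PFS estimate may be slightly less favourable than under the literal rule, and it will agree with the plan's own definition. OS needs no change.
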